2.3 Exploratory Objectives

- 2.3.1 To measure treatment-related tumor-specific immune response (immunogenicity).
- 2.3.2 To explore the immunological biomarkers (PD-L1 expression in tumor, DC-HIL expression in MDSC, TCR diversity and clonality, etc) as correlates or predictors for treatment response.
- 2.3.3 To evaluate the cost-effectiveness and cost-utility of the addition of SABR to Nivolumab in patients with mRCC

2.4 Endpoints

- 2.4.1 **Response:** Treatment response will be measured using both the RECIST and immune related RECIST criteria (ir-RECIST), a minor modification of RECIST 1.1 for immunotherapy [89]. Radiated lesions will be excluded from target lesions.
- 2.4.2 **Death:** Death due to any cause, although in mRCC patient population, the overwhelming majority is expected to be secondary to disease progression.
- 2.4.3 **Progression:** Progression will be defined according to the ir-RECIST criteria and verified by a second set of imaging at least 6 weeks apart.
- 2.4.4 **Immune Response:** Immune response will be measured using ELISpot assay, T-cell proliferation assay and ELISA.
- 2.4.5 **Toxicity:** Toxicity will be measured using CTAE v4.0

- 2.4.6 HR-QoL:** HR-QoL will be measured using FACT-G, EQ-5D and FKSI questionnaires at baseline, and at different time-points during treatment and follow up
- 2.4.7 Cost-effectiveness analysis:** Health care utilization data needed to assess costs will be obtained from patients' insurance claims during and after treatment. Markov modeling with probabilistic sensitivity analysis will be used to correlate quality-adjusted survival and cost.

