2.2 Secondary Objectives

- 2.2.1 RR based on ir-RECIST
- 2.2.2 To evaluate overall survival (OS), which is defined as the time between date of registration and the date of death due to any cause. In analyzing OS, we will take into account the MSKCC prognostic criteria for mRCC and compare our data to historical controls in the appropriate risk category
- 2.2.3 To evaluate progression free survival (PFS), which is defined as the time between date of registration and the first date of documented disease progression or date of death due to any cause
- 2.2.4 To evaluate complete response rate, which is defined as the percentage of patients who show complete response as per ir-RECIST criteria
- 2.2.5 To evaluate time to progression (TTP), which is defined as time between date of registration and date of documented progression.
- 2.2.6 To evaluate median response duration, which is defined as the time between the date a response (CR or PR) was first seen until date of progression
- 2.2.7 To evaluate the tolerability and toxicity as measured according to CTCAE v4.0.
- 2.2.8 To measure the improvement in health-related quality of life (HR-QoL)

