For Grade 3 or Grade 4 symptoms: (Severe reaction, Grade 3: prolonged [ie, not rapidly responsive to symptomatic medication and/or brief interruption of infusion]; recurrence of symptoms following initial improvement; hospitalization indicated for other clinical sequelae [eg, renal impairment, pulmonary infiltrates], Grade 4: life-threatening; pressor or ventilator support indicated) Immediately discontinue infusion of Nivolumab. Begin an IV infusion of normal saline, and treat the subject as follows: Recommend bronchodilators, epinephrine 0.2 to 1 mg of a 1:1,000 solution for subcutaneous administration or 0.1 to 0.25 mg of a 1:10,000 solution injected slowly for IV administration, and/or diphenhydramine 50 mg IV with methylprednisolone 100 mg IV (or equivalent), as needed. Subject should be monitored until the investigator is comfortable that the symptoms will not recur. Nivolumab will be permanently discontinued. Investigators should follow their institutional guidelines for the treatment of anaphylaxis. Remain at bedside and monitor subject until recovery from symptoms. In the case of late-occurring hypersensitivity symptoms (eg, appearance of a localized or generalized pruritus within 1 week after treatment), symptomatic treatment may be given (eg, oral antihistamine or corticosteroids).

Continued Treatment Beyond Progression of Disease

As indicated above, we will use the RECIST and ir-RECIST criteria for tumor measurement and RR determination. Accordingly, an initial progression on the first set of scans should be verified by a second set of scans before considering it as disease progression and before the decision to discontinue treatment is made. If progression is confirmed on the second set of scans, the first date will be used in evaluations of PFS. (Scans are collected at the time points listed in the study procedures)

In addition, accumulating evidence indicates a minority of subjects treated with immunotherapy may derive clinical benefit from continued treatment despite initial evidence of progressive disease. For this reason, subjects will be permitted to continue study therapy beyond initial investigator-assessed ir-RECIST) progression as long as they meet the 2 criteria listed below at the discretion of the treating medical oncologist:

- Investigator-assessed clinical benefit,
- and
- Subject is tolerating study drug.

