Subjects should discontinue study therapy upon evidence of further progression at the discretion of the treating medical oncologist, defined as an additional 10% or greater increase in tumor burden from time of initial progression (including all target lesions and new measurable lesions).

New lesions are considered measurable at the time of initial progression if the longest diameter is at least 10 mm (except for pathological lymph nodes, which must have a short axis of at least 15 mm). Any new lesion considered non-measurable at the time of initial progression may become measurable and therefore included in the tumor burden measurement if the longest diameter increases to at least 10 mm (except for pathological lymph nodes, which must have an increase in short axis to at least 15 mm). For statistical analyses that include the investigator-assessed progression date, subjects who continue treatment beyond initial investigator-assessed, ir-RECIST 1.1-defined progression will be

considered to have investigator-assessed progressive disease at the time of the initial progression event.

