6.0 Measurement of Effect

6.1 Antitumor Effect

Response and progression will be evaluated in this study using the new international criteria proposed by the Response Evaluation Criteria in Solid Tumors (RECIST) Committee [JNCI 92(3):205-216, 2000]. The only change from RECIST v.1.1 being implemented in this study is a confirmation of new lesions or progressive disease (PD) by a second scan >6 weeks apart, based on the immune RECIST (ir-RECIST) criteria proposed by Wolchok. *et. al* that is appropriate for immune-related treatment response [89]. This is primarily because immune response often can take longer time as compared to chemotherapy before producing a radiographic response and during this time new lesions may arise which will eventually regress. If it were not for a second confirmation, these patients would be labeled to have failed therapy. Additional criteria for bone lesions and clinical endpoints of pathologic fracture and cord compression are added to this study (see Section 6.1.4). Changes in only the largest diameter (unidimensional measurement) of the tumor lesions are used in the RECIST v1.1 criteria outlined in <http://www.recist.com/>. The primary endpoint will be evaluated using RECIST v1.1 and secondary endpoint will be ir-RECIST.

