6.1.4 Response Criteria

6.1.4.1 Evaluation of Target Lesions

Complete Response (CR): Disappearance of all target lesions, determined by two separate observations conducted no less than 4 weeks apart. Any pathological lymph nodes must have reduction in short axis to < 10 mm. There can be no appearance of new lesions.

Partial Response (PR): At least a 30% decrease in the sum of the longest diameter (LD) of target lesions, taking as reference the baseline sum LD. There can be no appearance of new lesions.

Progressive Disease (PD): At least a 20% increase in the sum of the LD of target lesions, taking as reference the smallest sum LD recorded since the treatment started, or the appearance of one or more new lesions verified by a second scan > 6 weeks apart. In addition to the relative increase of 20%, the sum must also demonstrate an absolute increase of at least 5 mm.

Stable Disease (SD): Neither sufficient shrinkage to qualify for PR nor sufficient increase to qualify for PD, taking as reference the smallest sum LD since the treatment started.

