6.1.7 Progression-Free Survival

Progression-free survival (PFS) is defined as the duration of time from the date of registration to time of progression or date of death due to any cause.

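### PFS is tested against a historical nivolumab benchmark that is at least partly RECIST, while the trial's own progression rules differ on whether a second scan is needed, so the same scans can give different event counts

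*Combined protocol and SAP*

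**What the plan says.** **The test.** The Study Summary (Statistical Methodology) and section 11.3 plan one-sample log-rank tests of PFS and OS against historical control. The Study Summary names the reference as nivolumab alone from a published phase III study. Section 11.3 gives no null curve, alpha or sidedness for PFS. The two-sided 0.2 in section 11.2 belongs to the response-rate test.

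**The benchmark.** Section 1.4.2 gives historical PFS medians of 4-4.6 months from two cited trials. Section 2.1 gives phase II medians of 2.7, 4.0 and 4.2 months by RECIST for three dose groups, and 4.3, 5.4 and 6.9 months for the same groups by immune-response PFS.

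**Rules that require a second scan.**
- Section 2.4.3: "Progression will be defined according to the ir-RECIST criteria and verified by a second set of imaging at least 6 weeks apart".
- Section 4.2.1.1: "an initial progression on the first set of scans should be verified by a second set of scans before considering it as disease progression". The event is then backdated: "If progression is confirmed on the second set of scans, the first date will be used in evaluations of PFS".
- Section 6.1 gives as its one change from RECIST 1.1 "a confirmation of new lesions or progressive disease (PD) by a second scan >6 weeks apart".

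**Rules that do not, or that are unclear.**
- Section 4.2.1.1, on statistical analyses that use the progression date: patients treated beyond initial progression are "considered to have investigator-assessed progressive disease at the time of the initial progression event", with no confirmation condition.
- Section 6.1.4.1: target-lesion progression is a 20% increase "or the appearance of one or more new lesions verified by a second scan > 6 weeks apart". The second scan may govern both parts or only new lesions.
- Section 6.1.4.2 and the table in 6.1.4.3 count new lesions and non-target progression with no second scan mentioned. Section 6.1.4.4.1 does require a repeat scan for new bone lesions.
- Sections 6.1.4.5 and 6.1.4.6 add pathologic fracture (except at a treated site) and cord or cauda equina compression as progression.

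**The concern.** A one-sample log-rank test compares observed events with the number expected under a null curve. The comparison is fair only if the trial and the benchmark count the same thing as an event.

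Consider a patient whose first scan shows RECIST progression and whose second scan does not confirm it. Section 2.1 expects such patients, because it describes tumour flare. A RECIST benchmark counts that patient as an event at the first scan. The second-scan rules do not: the patient stays at risk until a later event, which adds expected events without adding an observed one. A positive PFS result could then partly reflect the progression rule. If the analyst instead follows the treated-beyond-progression paragraph, the same patient is an event at the first scan. The plan does not say which applies.

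**Working it through.** **1. The plan's own figure.** No PFS sample size, power or alpha is stated, so there is none to reproduce. The response-rate figure in section 11.2 does reproduce: with n = 19, 25% against 50% and at most 0.10 in each tail, the rule is 8 or more responses, with upper-tail error 0.0775 and power 0.820 (n = 18 gives 0.760). It does not bear on PFS.

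**2. Where the mismatch arises.** Confirmed progressions take the first-scan date, so they match a RECIST benchmark. Only first progressions that are never confirmed differ.

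**3. Test statistic.** Z = (O − E)/√E, where O is observed events and E is (ln 2 / null median) × total time at risk, for an exponential null. Benefit is declared at Z < −1.96.

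**4. Hand approximation (no censoring, no SABR effect).** Let p be the share of first progressions never confirmed, and d the median added time to the later event as a multiple of the null median. Then E ≈ 19(1 + pd) and O ≈ 19.
- p = 0.05, d = 0.5: E = 19.475, Z ≈ −0.475/4.413 = −0.11.
- p = 0.10, d = 1: E = 20.9, Z ≈ −1.9/4.572 = −0.42.
- p = 0.20, d = 2: E = 26.6, Z ≈ −7.6/5.158 = −1.47.

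Fracture and cord events act the other way. If they add 10% to the hazard and p = 0, E ≈ 19/1.1 = 17.27 and Z ≈ 1.73/4.156 = +0.42, about enough to cancel the second case.

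**5. Simulation.** Inputs: n = 19; null median 4.6 months; no SABR effect; uniform censoring at 36-96 months (5-year accrual plus 3-year follow-up, Study Summary). Assumed, because the documents do not give them: two-sided 0.05, exponential times, p, d and the added fracture/cord hazard. Each cell is the probability of declaring benefit for d = 0.5 / 1 / 2.

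| Never confirmed | No added hazard | +5% hazard | +10% hazard |
|---|---|---|---|
| 0% (matched in the first column) | 1.5% | 0.8% | 0.4% |
| 5% | 1.9 / 2.7 / 5.5% | 1.0 / 1.4 / 3.1% | 0.5 / 0.7 / 1.7% |
| 10% | 2.5 / 4.3 / 11.7% | 1.3 / 2.4 / 7.0% | 0.7 / 1.3 / 4.0% |
| 20% | 3.7 / 9.6 / 29.4% | 2.1 / 5.6 / 19.6% | 1.1 / 3.2 / 12.5% |

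Of the 27 mismatch cells, 13 are at or below the nominal 2.5% upper tail, and 8 are below the matched 1.5%.

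**6. The unstated null.** With matched criteria, a null of 4.0 and a true median of 4.6 gives E ≈ 19 × 4.6/4.0 = 21.85, Z ≈ −0.61 and 7% false benefit. A null of 4.6 and a true median of 4.0 gives E ≈ 16.52, Z ≈ +0.61 and 0.2%.

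**The case against.** The strongest reply is that the treated-beyond-progression paragraph is the one place that speaks of statistical analyses. If it counts every initial progression, patients treated through flare are events at the first scan and most of the lean disappears. This stands for that reading. But the paragraph can also be read as repeating the backdating of confirmed progressions, and nothing in the plan chooses between the two.

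Second, the conflict can be drawn too widely. Section 2.2.3 ("first date of documented disease progression or date of death due to any cause") and section 6.1.7 ("duration of time from the date of registration to time of progression or date of death due to any cause") state no confirmation rule, but they rely on the term that section 2.4.3 defines and are not separate contradictions. Section 6.1 may also be meant to govern all of 6.1.4. This narrows the problem to the two paragraphs of 4.2.1.1, the wording of 6.1.4.1, and whether 6.1.4.2 and the table in 6.1.4.3 inherit the confirmation rule.

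Third, the medians labelled RECIST come from the phase II trial, not the named phase III comparator. This stands, so the mismatch with that comparator is likely but not shown. It also weakens the 4.0-month null as an example, since 4.0 matches a phase II arm.

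Fourth, PFS is one of several secondary endpoints in a small single-arm trial sized on response rate, and Kaplan-Meier estimates with 95% intervals are planned anyway. This limits the weight of the point. It does not remove it while a formal test is planned.

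**Conclusion.** The point holds in a limited form. The progression rules can give different PFS event counts from the same scans, and on the second-scan reading the test can lean towards SABR relative to a RECIST benchmark. The conflict between the rules needs no assumption. The size of the lean is unknown: the range of about 0.5% to 29% false benefit, against 1.5% when matched, rests entirely on assumed inputs, and the top figure needs 20% never confirmed, a long added delay and no fracture or cord events.

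Three stronger readings are not supported:
- **That the bias is established and large.** A reader might put the section 2.1 shift (4.0 to 5.4 and 4.2 to 6.9 months) into the test and obtain roughly 23% to 55% false benefit. The dating rule behind those immune-response medians is not stated, and this trial backdates confirmed events, so the shift shows direction only.
- **That confirmation delays every event by six weeks.** Backdating to the first scan rules this out.
- **That the named comparator's PFS is known to be RECIST, or that the primary result is affected.** The comparator's criteria are not stated, and response rate is assessed separately by RECIST 1.1.

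**What to change.** For the historical comparison, define a PFS event as RECIST 1.1 first progression without confirmation, or death, using the RECIST assessments already planned in section 5.3. Report PFS by confirmed ir-RECIST descriptively or as a sensitivity analysis. Do the same for PFS that includes fracture and cord compression events that are not RECIST progression.

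Reconcile the analysis wording in sections 2.4.3, 4.2.1.1, 6.1 and 6.1.4.1 to 6.1.4.6. In section 11.3, state which curve from the phase III comparator is the null, the progression criteria behind it, and the alpha with its sidedness. Stating the null and alpha alone would not cure the event mismatch.

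The cost is protocol and SAP wording, with no extra scans or data. The downside is that PFS will look shorter than under confirmed ir-RECIST. The change concerns the analysis definition only and leaves treatment decisions as they are.

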3.0 Subject ELIGIBILITY

Subjects must meet all of the inclusion and exclusion criteria to be registered to the study. Study treatment may not begin until a subject is registered.

3.1 Inclusion Criteria

- 3.1.1 At least 18 years of age
- 3.1.2 Willing and able to provide consent
- 3.1.3 Pathologic diagnosis of metastatic RCC with clear cell component with progression or intolerance to at least one prior systemic anti-angiogenic therapy
- 3.1.4 Measurable disease in at least 1 non-radiated sites.
- 3.1.5 Eligible for extra-CNS SAbR to 1-6 sites of disease
- 3.1.6 Must have received at least one prior anti-angiogenic therapy (or inability to tolerate, as above) in the advanced or metastatic setting. Prior cytokine therapy (eg, IL-2, IFN- α), vaccine therapy, or treatment with cytotoxics is also allowed but not any other drug specifically targeting T-cell co-stimulation or checkpoint pathways.
- 3.1.7 Previous treatment with surgery, radiation, chemotherapy, targeted agents (see above) are allowed provided that:
- 3.1.7.1 Chemotherapy/Major surgery was administered > 7 days before the start Nivolumab
- 3.1.7.2 Minor surgery, radiation, or any targeted agents were administered before the start of Nivolumab
- 3.1.8 Performance Status (ECOG 0 - 3 OR Karnofsky 100 - 30)
- 3.1.9 Women of child-bearing potential (WOCBP):
- A female of child-bearing potential is any woman (regardless of sexual orientation, having undergone a tubal ligation, or remaining celibate by choice) who meets the following criteria:
 - Has not undergone a hysterectomy or bilateral oophorectomy; or
 - Has not been naturally postmenopausal for at least 12 consecutive months (i.e., has had menses at any time in the preceding 12 consecutive months).
 - WOCBP must have a negative serum or urine pregnancy test at screening and within 24 hours prior to the start of investigational product.
 - Women must not be breastfeeding.
 - WOCBP must agree to use adequate contraception (hormonal or barrier method of birth control; abstinence) prior to study entry, for the duration of study participation and contraception should be continued for a period of 90 days plus

the time required for the investigational drug to undergo five half-lives. This is equivalent to 31 weeks after discontinuation of Nivolumab.

- Should a woman become pregnant or suspect she is pregnant while participating in this study, she should inform her treating physician immediately.

3.1.10 Men who are sexually active with WOCBP must use any contraceptive method with a failure rate of less than 1% per year. Contraception should be continued for a period of 90 days plus the time required for the investigational drug to undergo five half-lives. This is equivalent to 31 weeks after discontinuation of Nivolumab.

3.2 Exclusion Criteria

- 3.2.1 Subjects who have had major surgery (such as nephrectomy) or chemotherapy within 7 days (or at the discretion of the treating medical oncologist) prior to first dose of drug
- 3.2.2 Subjects who have had radiation therapy within 1 week prior to first dose of drug
- 3.2.3 Uncontrolled adrenal insufficiency or active chronic liver disease
- 3.2.4 Any history of CNS metastases that is not adequately treated with surgery or SABR >14 days prior.
- 3.2.5 Prior treatment with any anti-PD-1, anti-PD-L1, anti-PD-L2, anti-CD137, or anti-CTLA-4 antibody, or any other antibody or drug specifically targeting T-cell co-stimulation or checkpoint pathways.
- 3.2.6 Any positive history for HIV/AIDS, HTLV, hepatitis B or hepatitis C virus indicating acute or chronic infection.
- 3.2.7 Any active known or suspected autoimmune disease. Subjects with vitiligo, type I diabetes mellitus, residual hypothyroidism due to autoimmune condition only requiring hormone replacement, psoriasis not requiring systemic treatment, or conditions not expected to recur in the absence of an external trigger are permitted to enroll.
- 3.2.8 Any condition requiring systemic treatment with either corticosteroids (> 10 mg daily prednisone equivalent) or other immunosuppressive medications within 14 days prior to the first dose of study drug. Inhaled steroids and adrenal replacement steroid doses up to 10 mg daily prednisone equivalent are permitted (although not encouraged) in the absence of active autoimmune disease.
- 3.2.9 Subjects with life expectancy < 6 months
- 3.2.10 Subjects receiving any other investigational or standard antineoplastic agents.
- 3.2.11 Prior malignancies active within the previous 3 years except for locally curable cancers that have been apparently cured, such as basal or squamous cell skin cancer, superficial bladder cancer, or carcinoma in situ of the prostate, cervix, breast, or etc.
- 3.2.12 Psychiatric illness/social situations that would limit consenting and compliance with study requirements.

3.2.13 Patients with history of hypersensitivity to monoclonal antibodies

3.2.14 Subjects who are pregnant or nursing due to the potential for congenital abnormalities and the potential of this regimen to harm nursing infants.

4.0 TREATMENT PLAN

4.1 SABR Dose and Techniques

Patients should have at least 1 measurable non-CNS lesions. Lesions receiving SABR will be called “radiated” lesions. “Target” lesions will be selected from non-treated lesions. In any case, there should be at least one (non-CNS) measurable lesion for effect measurement. Prior irradiated lesions (outside of the trial) will be excluded from target lesions. SABR will be administered to 1-6 sites of metastatic disease on the 2 weeks after the second dose of Nivolumab with a single (24-27 Gy) or three (11-16 Gy/fraction) fractions. The sites of larger (bulky) disease and the sites of symptomatic disease will be prioritized for treatment.

